5. STATISTICAL CONSIDERATIONS

A. Sample size

The sample size estimates depend in large part on the standard deviation (SD) for logMAR UCIVA. Assuming a SD of 0.12 (from a previous Eyhance study), for the two-sided t-test (alpha =0.05) for the intermediate visual acuity endpoint, we will need 31 subjects in each group (emmetropia / mini monovision) to detect differences of 0.1 logMAR (1 line difference) with 90% power. Total sample size = 62. Allowing 10 % for the potential confounding factor of having 2 sites, and 10% assumed dropout rate, 74 subjects will be enrolled (37 in each group). Table 2 summarizes the sample size estimate.

Table 2. Sample size estimate.

	TOTAL	Mini monovision	Emmetropia
Sample size	62	31	31
10% multiple sites	6	3	3

10% dropout rate	6	3	3
Total sample size	74	37	37

B. Statistical Analysis

All data will be collected by the site and entered into a database. Subjects will be assigned an ID number. Data analysis will be performed without patient identification. Statistical analysis will be performed using standard descriptive statistics and other tests as deemed appropriate based on the characteristics of the data to be analyzed. All statistical tests will be two-sided and interpreted at a 5% significance level. Comparisons between the groups will be made. Data analysis will be conducted by a third-party consultant.

C. Study Endpoints:

Comparisons between the groups:

1. Primary Endpoints:

Binocular distance-corrected intermediate (66 cm) visual acuity at 3 months. Distance corrected. DC, for the purpose of this study, is defined as corrected for the target refraction (i.e. emmetropia OU corrected for plano. Mini monovison dominant eye corrected for plano and the non-dominant eye for -0.75).

2. Secondary Endpoints:

- 1. Binocular defocus curve at 3 months
- 2. Binocular low contrast distance visual acuity at 3 months
- 3. Uncorrected and distance-corrected near (40 cm) visual acuity at 1 and 3 months
- 4. Uncorrected and distance-corrected intermediate (66 cm) visual acuity at 1 and 3 months
- 5. Uncorrected and best-corrected distance (4 m) visual acuity at 1 and 3 months
- 6. Distance-corrected near visual acuity at best distance at 3 months
- 7. To evaluate patient's overall satisfaction of their vision
- 8. To evaluate patient's spectacle independence
- 9. To evaluate visual symptoms using a questionnaire.
- 10. Residual mean spherical equivalent refraction at 3 months
- 11. Residual refractive sphere at 3 months
- 12. Residual refractive cylinder at 3 months
- 13. Percentage of eyes with postoperative MRSE accuracy to target ≤ 0.5D at 3 months

D. Safety Analyses

The type, severity, duration and frequency of reported ocular adverse events will be tabulated for each group. Adverse events will also be summarized for events that were considered

[name] 10

treatment-related. Comparison of treatment groups with respect to the proportion of study patients reporting adverse events will be made using Fisher's Exact Test.

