Potential subjects will be identified from the patients presenting at the clinic. Additionally, an ad will be placed in social media and in the practice website, if deemed necessary. Once identified as a study candidate, the patient will be asked if he/she would like to participate. The sub-investigator, study coordinator or an appropriately trained staff member will answer any and all questions and will obtain informed consent. A copy of the signed informed consent document will be given to the subject. The principal investigator will be available if the subject wants to discuss further details with him. Any testing that is part of the investigative site's standard preoperative cataract evaluation may be performed prior to the informed consent being signed, provided these tests are conducted within 90 days of surgery. The patient will understand that participation in the study, or declining to participate, will not affect his/her quality of care.

No subject will be enrolled into the study that does not meet the inclusion/exclusion criteria and does not sign the current approved informed consent document. Informed consent will be obtained prior to collecting any data for the study. The original signed documents will be maintained by the investigator as a permanent part of the subject's research records.

B. Surgery Procedures:

Patients will be randomized to one of two groups:

- Group A, plano OU. The target refraction for both eyes will be emmetropia (± 0.25 D).
- Group B, mini monovision. The target refraction for the dominant eye will be plano (± 0.25 D) and for the non-dominant eye between -0.75D ±0.15.

C. Study Visit Schedule and Assessments (Table 1).

- **1. Visit Schedule:** Subjects will be examined at the following intervals:
 - 1. Visit 1: Screening and enrollment: Preoperative evaluation completed not more than eight weeks before surgery
 - 2. Visit 2: Day of Surgery
 - 3. Visit 3: Day 1: (12 to 48 hours) after surgery
 - 4. Visit 4: Month 1: 30 ±7 days postoperative after second eye surgery
 - 4. Visit 5: Month 3: 90 ±15 days postoperative after second eye surgery

D. Measurements and evaluations

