- 5. Visit 5: Slit lamp examination, manifest refraction, binocular UCDVA, BCDVA, UCIVA (at 66 cm), DCIVA (at 66 cm), DCNVA (at 40 cm), DCNVA (at 40), and DCNVA at best distance, binocular low contrast (10%) photopic and mesopic BCDVA, DC binocular defocus curve, IOL orientation (if toric lens) and dilated fundus exam as deemed necessary by the investigator, patient satisfaction, visual symptoms and spectacle independence questionnaires, and any device deficiencies.

DC: distance corrected. DC, for the purpose of this study, is defined as corrected for the target refraction (i.e. emmetropia OU corrected for plano. Mini monovison dominant eye corrected for plano and the non-dominant eye for -0.75).

All adverse events and complaints will be monitored and recorded at all study visits.

Table 1. Visits and Study Assessments

	Visit 1 Screening	Visit 2/2A DOS	Visit 3/3A POD #1	Visit 4 1-Month	Visit 5 3-Month
Informed Consent	Х				
Inclusion/Exclusion	Х				
Demographics/PMH/Ocular history	Х				
Eye dominance	Х				
BCVA (Standard of care, Snellen)	Х				
UCVA (Standard of care, Snellen)			Х		
UCVA ETDRS (4m)				X*	X**
Manifest refraction – Max Plus				Х	Х
BCVA ETDRS (4m)				X*	X**
UCIVA ETDRS (66 cm)				X*	X**
DCIVA ETDRS (66 cm)				X*	X**
UCNVA ETDRS (40 cm)				X*	X**
DCNVA ETDRS (40 cm)				X*	X**
DCNVA at best distance					X**
DCVA Photopic low contrast (10%)					X**
DCVA Mesopic low contrast (10%)					X**
Defocus curve					X**
Intraocular Pressure (Standard of care)	Х		X	Χ	
SLE	Х		X	Χ	Х
Dilated fundus exam	Х			X [‡]	X [‡]
Cataract density / type	Х				
Corneal topography¥	Х				
Intraoperative data		Χ			
Toric IOL position		X^{\dagger}	X [†] ±	X ^{†±}	X [‡]
Questionnaires	Х			Χ	Х
AE/Device deficiencies		Χ	Х	X	Х

X To be performed as scheduled

^{*} Monocular and binocular testing

^{**} Binocular testing only

[‡] To be performed as deem necessary by the investigator.

[†] If toric lens

[¥] If astigmatism correction (toric or corneal arcuates)

DC: distance corrected. DC, for the purpose of this study, is defined as corrected for the target refraction (i.e. emmetropia OU corrected for plano. Mini monovison dominant eye corrected for plano and the non-dominant eye for -0.75).

8

4. Study endpoint criteria

- A. Patient Completion of Study: If a study patient has completed the final visit (Visit 5) of the study, he/she is considered to have completed the study.

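### Was the trial sized on uncorrected intermediate acuity although its primary endpoint is distance-corrected?

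*Combined protocol and SAP*

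**What the plan says.** Section 5.A (Sample size) begins: "The sample size estimates depend in large part on the standard deviation (SD) for logMAR UCIVA". It continues: "Assuming a SD of 0.12 (from a previous Eyhance study), for the two-sided t-test (alpha =0.05) for the intermediate visual acuity endpoint", and arrives at 31 subjects per group for 90% power to detect 0.1 logMAR. Table 2 adds 3 per group for having two sites and 3 per group for dropout, giving 37 per group and 74 in all.

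Section 5.C.1 lists one primary endpoint: "Binocular distance-corrected intermediate (66 cm) visual acuity at 3 months". Uncorrected intermediate acuity (UCIVA) appears only under 5.C.2, item 4: "Uncorrected and distance-corrected intermediate (66 cm) visual acuity at 1 and 3 months".

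The two measures are recorded separately. The Visit 5 list in Section 3.D includes "binocular UCDVA, BCDVA, UCIVA (at 66 cm), DCIVA (at 66 cm"), and the Table 1 footnote for that visit reads "Binocular testing only". The plan also gives distance correction its own meaning: "DC, for the purpose of this study, is defined as corrected for the target refraction". The non-dominant eye in the mini-monovision group therefore keeps its -0.75 D offset during distance-corrected testing.

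**The concern.** By its own account the sample size rests largely on one SD, and that SD is labelled with a measure that is not the primary endpoint. Section 5.A never names DCIVA. It does not say whether 0.12 is a monocular or a binocular value, and it describes the source only as earlier work with the lens. Either UCIVA is a slip for DCIVA, or the UCIVA value stands in for DCIVA without the plan saying so. The documents do not settle which.

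At stake would be the 90% power claim. Required sample size grows with the square of the SD, so if DCIVA varied more than 0.12, 31 per group would fall short.

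**Working it through.** **Step 1. Which endpoint was powered?** Section 5.A refers to one intermediate acuity endpoint, in the singular. Section 5.C.1 has one primary endpoint, and it is an intermediate acuity. The competing reading is that the trial was sized on part of secondary item 4, which combines two measures at two visits. That is strained. What remains is the word UCIVA attached to the SD.

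**Step 2. Reproduce the plan's figure.** Inputs, all from 5.A: SD 0.12, difference 0.1 logMAR, two-sided alpha 0.05 (z = 1.960), power 90% (z = 1.2816), equal groups.

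- n per group = 2 × [(1.960 + 1.2816) × 0.12 / 0.1]² = 2 × (3.8899)² = 30.26, rounded up to 31. This agrees with the plan.
- Power at 31, normal approximation: 0.1 / (0.12 × √(2/31)) = 3.281; 3.281 − 1.960 = 1.321; power 90.7%.
- Power at 31, noncentral t with 60 df: 89.8%. The exact solution is 31.25, so 32 per group. The difference from 31 is trivial.
- Enrolment: 31 + 3 + 3 = 37 per group, 74 in total. Directly, 62 × 1.2 = 74.4.

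**Step 3. What if the DCIVA SD is not 0.12?** The documents give no such value, so the SDs below are assumptions. Power is by exact t at three analysed sizes: 31 (the calculated number), 34 (37 less the 3 allowed for dropout) and 37 (all enrolled).

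| Assumed SD | n per group for 90% (normal / exact t) | Power, n = 31 | Power, n = 34 | Power, n = 37 |
|---|---|---|---|---|
| 0.10 | 22 / 23 | 97.2% | 98.2% | 98.9% |
| 0.11 | 26 / 27 | 94.1% | 95.8% | 97.1% |
| 0.12 | 31 / 32 | 89.8% | 92.3% | 94.3% |
| 0.13 | 36 / 37 | 84.6% | 87.8% | 90.4% |
| 0.14 | 42 / 43 | 79.0% | 82.7% | 85.8% |
| 0.15 | 48 / 49 | 73.3% | 77.3% | 80.8% |

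With 34 per group analysed, power stays at 90% or more up to an SD of 0.125, and at 80% or more up to 0.145. The table runs in both directions. Nothing in the documents places the DCIVA SD above 0.12 rather than below it.

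**Step 4. Does the label reach the analysis?** No. A two-sample t-test on DCIVA estimates its variance from the trial's own data. The planning SD enters neither the test statistic nor the confidence interval, so a wrong label on it cannot bias the estimate or alter the type I error rate.

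**The case for a change.** The strongest case for acting is that this protocol treats the two measures as distinct. It lists them separately at Visits 4 and 5 and in Table 1, and it repeats its definition of distance correction. A plan that careful should say which kind of SD drives its sample size, and one or two sentences would do it. The table shows that the answer could matter: at an assumed SD of 0.14, power with 31 per group is 79.0%, not 90%.

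Part of this stands. The label in 5.A does not match 5.C.1, and the source and type of the SD are not traceable. It is also fair that nobody can show from these documents that 0.12 is right for DCIVA. Because distance correction here keeps the assigned target, UCIVA and DCIVA carry the same intended contrast between groups. That describes this study, however, and not the one that supplied the SD, so it does not prove that the two SDs are alike.

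What does not stand is the step from an untraceable label to a defect in the design. The losses in power come from SDs chosen for illustration. The proposed remedy would itself keep the sample size, the endpoint, the 0.1 logMAR difference and the test.

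**Conclusion.** The mismatch between UCIVA in 5.A and DCIVA in 5.C.1 is genuine but clerical: a wrong abbreviation, or a proxy that was not declared. An analyst would take the single primary endpoint in 5.C.1 as the powered one and test DCIVA. The plan's 31 per group and 90% power reproduce from its stated inputs (90.7% by normal approximation, 89.8% by exact t), and no figure in the plan is shown to be wrong.

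This conclusion rests on two things: that 5.A refers to the sole primary endpoint, and that no DCIVA SD is available in the documents to contradict 0.12. A sourced DCIVA SD clearly above about 0.125 would raise a real question about power, but it would be a different point, resting on evidence that the documents do not contain. As things stand, relabelling the SD improves traceability and changes nothing in the design, the analysis or the interpretation. No change to the plan is called for.

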Monofocal lenses correct only at the target distance chosen (i.e., distance without intermediate or near vision improvement or near without distance improvement). Intermediate vision has become important for many daily activities such as reading a mobile phone or tablet. Tecnis Eyhance IOL, recently approved by the FDA,^A is a new generation of monofocal lenses designed to improve and/or enhance intermediate vision without compromising the distance vision with low incidence of halo, glare or starburst. Auffarth et al¹ in a study that included 67 patients implanted bilaterally with the Eyhance IOL showed an improvement of 1 line of intermediate visual acuity compared to a standard monofocal IOL (ZCB00). Additionally, they reported no differences between the 2 groups in contrast sensitivity and visual disturbances complains.

The purpose of this study is to evaluate the visual outcomes of a monofocal IOL with an enhanced intermediate function, in patients with or without astigmatism, when both eyes are targeted for emmetropia and when the non-dominant eye is targeted for mini monovision (-0.75 D) in patients undergoing routine cataract surgery.

1. OBJECTIVE:

CONFIDENTIAL

The main objective of this study is to evaluate the visual outcomes of a monofocal IOL with an enhanced intermediate function, in patients with or without astigmatism, when both eyes are targeted for emmetropia and when the non-dominant eye is targeted for mini monovision (-0.75 D) in patients undergoing routine cataract surgery.

2. STUDY DESIGN AND METHODS:

- A. Test article: Tecnis Eyhance Intraocular lens Toric (DIUxxx) and non-toric (DIB00)
- **B. Study Design:** Prospective, multicenter (up to 2 sites in USA), randomized, patient-masked bilateral eye study.
- C. **Subjects:** A total of 74 subjects who met the Inclusion/Exclusion criteria will be enrolled.

1. Inclusion Criteria:

Subjects **MUST** fulfill the following conditions to qualify for enrollment into the trial

- 1. Subject is undergoing bilateral cataract extraction with intraocular lens implantation.
- 2. Gender: Males and Females.
- 3. Age: 50 years and older.
- 4. Willing and able to provide written informed consent for participation in the study
- 5. Willing and able to comply with scheduled visits and other study procedures.
- 6. Scheduled to undergo standard cataract surgery in both eyes within 6 30 days between surgeries.
- 7. Subjects who require an IOL power in the range of +5.0 D to +34.0 D only.

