1. Visit 1: Informed consent process will be conducted at this visit. Assessments include best-corrected distance visual acuity (BCDVA, Snellen chart), manifest refraction, intraocular pressure (IOP), corneal topography (if astigmatism correction), eye dominance, slit lamp examination including dilated fundus exam, cataract density and type. Any testing that is part of the site's standard of care preoperative cataract surgery evaluation may be performed prior to the informed consent being signed provided these tests are conducted within 90 days of the surgery and notation of the date performed is entered onto the CRF. The surgeon's standard pre cataract surgery treatment will be used in all his patients

Each subject will be randomized to Group A (emmetropia OU) or B (mini monovision). Randomization will ensure that an equal number of subjects are enrolled in each group.

- Visit 2: The surgeon may use his preferred small incision cataract extraction technique (manual phacoemulsification or laser assisted). The assigned lens will be implanted in the bag. The following information will be captured the day of surgery: phaco technique (manual or laser), lens implanted and power, target refraction for IOL power implanted, additional surgical procedures, intraoperative complications, and any device deficiencies. The surgeon's standard post cataract surgery treatment will be used in all his patients. IOL power changes based on intraoperative aberrometry (i.e., ORA) are not allowed.
- 3. Visit 3: monocular UCVA (Snellen), slit lamp examination, IOP, and lens orientation (if toric lens and deem necessary by the investigator) and any device deficiencies.
- 4. Visit 4: Slit lamp examination, manifest refraction, monocular and binocular UCDVA, BCDVA, UCIVA (at 66 cm), DCIVA (at 66 cm), UCNVA (at 40 cm), and DCNVA (at 40), IOP, IOL orientation (if toric lens) and dilated fundus exam as deemed necessary by the investigator, patient satisfaction, visual symptoms and spectacle independence questionnaires, and any device deficiencies.

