8. INVESTIGATIONAL PRODUCT

A. Description

The Eyhance IOLs (DIB00 and DIUxxx) are monofocal refractive IOLs designed to enhance intermediate distance vision without compromising distance vision. The lens power continuously increases from its edge to the center extending the range of vision when compared to a standard monofocal IOL.

B. Treatment/Dosing Regimen

The Tecnis Eyhance IOL is intended for primary implantation for the visual correction of aphakia secondary to removal of a cataractous lens in adult patients. The IOL will be implanted at time of uncomplicated routine cataract surgery. Intraocular lenses are implantable medical devices and are intended for long term use over the lifetime of the patient.

C. Method for Assigning Subjects to Treatment/Dosing Groups

Each site will be provided with randomization envelopes. The envelopes will be sequentially numbered.

D. Subject Compliance Monitoring

Since the IOL is implanted at time of cataract surgery, subject compliance will not be an issue in this particular study.

E. Packaging, Receiving, Storage, Dispensing and Return

An account will be set up with the manufacturer of the lens (Johnson and Johnson Vision) that will provide the lens at no cost to the participants. IOLs will be ordered once the subject's qualification for the study has been confirmed. IOLs will be shipped to the site and will be stored and dispensed following the routine standard of care for cataract surgery. Unused IOLs will be returned to Johnson and Johnson Vision following their instructions.

Or, Johnson and Johnson Vision will provide a consignment of lenses that will be stored at the site and unused IOLs will be returned to Johnson and Johnson Vision following their instructions at the

end of the study.

In both instances, an implantation log will be kept.

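### Two-site concern is met only with 6 extra subjects; name a group-plus-site linear model as the primary comparison (modest gain, almost no cost)

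*Combined protocol and SAP*

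**What the plan says.** Section 2.B describes the study as "multicenter (up to 2 sites in USA"). Section 5.A sizes it "for the two-sided t-test (alpha =0.05) for the intermediate visual acuity endpoint", "Assuming a SD of 0.12 (from a previous Eyhance study"), and arrives at 31 per group for a 0.1 logMAR difference with 90% power. It then adds subjects, "Allowing 10 % for the potential confounding factor of having 2 sites". Table 2 shows this as 3 per group, 6 in total, followed by another 6 for dropout, giving 74.

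Section 5.B names no primary model and no covariate. It provides for descriptive statistics and "other tests as deemed appropriate based on the characteristics of the data to be analyzed". The only other named test is Fisher's exact test, for adverse events (5.D).

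On allocation, section 3.D (Visit 1) states: "Randomization will ensure that an equal number of subjects are enrolled in each group". Section 8.C states: "Each site will be provided with randomization envelopes", and "The envelopes will be sequentially numbered". Neither says whether each site's sequence is balanced between the groups. No section plans a site term.

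**The concern.** The plan calls site a confounder and answers with sample size. Had site been confounded with group, more subjects would not have removed the bias. Under randomisation it is not systematically confounded, so that label is too strong. Two smaller issues remain:

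- **Precision.** A difference between sites goes into the residual variance of a t-test that ignores site, and power falls. If the groups are balanced within site, the t-test is also conservative.
- **Chance imbalance.** If allocation is not balanced within site, one group may draw more from the better-performing site. The estimate in that trial is shifted, although the average over trials is not.

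A site term deals with both. Naming it now also means that nobody decides whether to adjust after seeing the data, a choice that 5.B currently leaves open.

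**Working it through.** **Inputs.** From 5.A: difference 0.10 logMAR, SD 0.12, two-sided alpha 0.05, 90% power, 31 per group plus 3 for sites. Assumed, because the documents are silent: a between-site gap in mean acuity of 0 to 0.10 logMAR, two equal sites, normal data.

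**Step 1: the plan's own figure.** n per group = 2 × (1.960 + 1.282)² × 0.12² / 0.10² = 30.3, so 31, as stated. Exact t-test power is 89.8% at 31 and 92.3% at 34 per group. The total 62 + 6 + 6 = 74 agrees with Table 2.

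**Step 2: what the 6 subjects buy.** With equal sites, a gap adds gap²/4 to the variance. Going from 31 to 34 per group offsets a gap of 2 × √(0.0144 × (34/31 − 1)) = 0.075 logMAR. The allowance is therefore a real precision reserve up to about that size.

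It does little for chance imbalance. With unstratified allocation, the SD of the difference in site share between groups is 1/√(N − 1): 1/√61 = 12.8 percentage points at N = 62 and 1/√67 = 12.2 at N = 68. At a gap of 0.10, a one-SD imbalance at N = 68 shifts the unadjusted estimate by 0.122 × 0.10 = 0.012 logMAR. A less typical split of 20 v 13 between groups of 33 shifts it by (7/33) × 0.10 = 0.021, about a fifth of the planned effect.

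**Step 3: t-test against a linear model on group and site.** Simulation with 200,000 trials per cell, 34 per group, true effect 0.10, both analyses fitted to the same data. Section 5.A does not say whether 0.12 includes between-site variation, so both readings are shown. Under the total-SD reading the within-site SD is √(0.0144 − gap²/4), that is 0.117 at a gap of 0.05 and 0.109 at 0.10. Entries are power, unadjusted / site-adjusted.

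| Reading of SD 0.12 | Site gap | Balanced within site | Unstratified |
|---|---|---|---|
| Either | 0 | 92.3% / 92.3% | 92.3% / about 91.9% |
| Within-site | 0.05 | 91.6% / 92.2% | 91.2% / 91.9% |
| Within-site | 0.075 | 90.8% / 92.3% | 89.9% / 91.9% |
| Within-site | 0.10 | 89.5% / 92.2% | 87.8% / 91.9% |
| Total | 0.05 | 92.8% / 93.4% | 92.3% / 92.9% |
| Total | 0.10 | 94.1% / 96.1% | 92.2% / 95.9% |

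The gain is 0.6 to 0.7 points at 0.05 and 2.0 to 4.1 points at 0.10. With sites split 2:1 it is 0.5 to 0.6 and 1.9 to 3.7 points.

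**Step 4: bias, error rate, interval width.** The mean unadjusted estimate was 0.100 in every cell, so there is no bias on average. Type I error of the t-test when balanced within site is about 4.6% at a gap of 0.05 and 3.1% to 3.4% at 0.10, against about 5.0% with the site term. When unstratified it is 4.9% to 5.1% throughout. At a gap of 0.10 the mean 95% CI half-width falls from 0.063 to 0.058 (within-site reading) or from 0.058 to 0.053 (total reading).

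**Step 5: cost.** With balance within site, the lost degree of freedom costs nothing visible (92.30% against 92.29% at 34 per group). If unstratified, the adjusted variance is inflated by 1/(1 − r²), where r is the difference in site share. The mean of r² is 1/67 = 1.5%, so 34 per group acts like 34 × 0.985 = 33.5. Power at 33 is 91.5% and at 34 is 92.3%, which puts the cost near the simulated 0.4 points (at most 0.5).

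**The case against.** The case for leaving the plan alone has substance.

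- **The gap is assumed, and there are reasons to expect a small one:** one lens family, common eligibility criteria, ETDRS testing at a fixed 66 cm, and a distance-corrected endpoint. With unstratified allocation and 0.12 within site, power is 92.0% unadjusted against 91.8% adjusted at a gap of 0.02, and 91.9% for both at 0.03. This stands: below about 0.03 there is no gain in that case.
- **The worst figure, 87.8%, needs three things at once:** unstratified allocation, 0.12 as the within-site SD, and a gap as large as the planned treatment effect. If 0.12 is the total SD, unadjusted power stays above 92%. This also stands.
- **The SD is stated for uncorrected acuity, while the primary endpoint is distance-corrected.** At 34 per group, t-test power would be 82.7% at an SD of 0.14 and 98.2% at 0.10 (illustrative values). That uncertainty exceeds the gain from a site term. The power levels above are therefore conditional on 0.12; the direction of the comparison is not affected.
- **A 10% loss from 37 leaves about 33 evaluable, not 34.** Unadjusted power at a gap of 0.075 is then 88.9% to 89.7% under the within-site reading. This is a small shift that slightly favours adjustment.
- **Section 5.B does not forbid a site term, and the wider gap is that no primary analysis is named.** Both are true, but permission is not prespecification, and the sponsor itself has singled out site as a concern.
- **Only one site may enrol.** Then the point falls away, and the proposed wording allows for it.

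**Conclusion.** The point holds as a low-cost improvement, not as an error that threatens the result. The 6 subjects are a sensible precision reserve for a site gap up to about 0.075 logMAR, but they do not adjust for site, and the plan contains nothing that does. There is no systematic bias and no inflation of type I error. The site term is worth well under 1 point of power at a gap of 0.05 and 2.0 to 4.1 points at 0.10. It also restores the nominal error rate if allocation is balanced within site, and removes the effect of chance site imbalance if it is not.

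These figures rest on an SD of 0.12, 34 evaluable per group, two equal sites, and site gaps that the documents do not supply. Confidence is medium, because the gain depends on a gap that cannot be known in advance.

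**What to change.** - **5.B, add:** *The primary comparison is a linear model of 3-month binocular distance-corrected intermediate acuity (66 cm) on group and site; the site term is omitted if only one site enrols. The adjusted difference and its 95% CI will be reported.*
- **5.A:** describe the 6 subjects as a precision reserve for between-site variation, not as a correction for confounding.
- **8.C:** state whether each site's envelope sequence is balanced between the groups.

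The first change carries the benefit; the other two make the text match what the extra subjects and the envelopes do. The cost is one sentence, one phrase and one clause, plus one degree of freedom in the analysis. No new data are needed, since site is known for every subject, and N stays at 74.

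### No primary model or missing-data rule is stated; the sized Month 3 t-test would drop patients without a Month 3 value, although binocular DCIVA is also measured at Month 1

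*Combined protocol and SAP*

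**What the plan says.** All places are in the combined protocol and SAP.

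- **Primary endpoint (Section 5.C.1):** "Binocular distance-corrected intermediate (66 cm) visual acuity at 3 months".
- **Sizing (Section 5.A):** the calculation is made "for the two-sided t-test (alpha =0.05) for the intermediate visual acuity endpoint", then enlarged for two sites and for dropout: "10% assumed dropout rate, 74 subjects will be enrolled (37 in each group".
- **Month 1 measurement (Section 3.D, Visit 4):** the list includes "monocular and binocular UCDVA, BCDVA, UCIVA (at 66 cm), DCIVA (at 66 cm". In Table 1 the row "DCIVA ETDRS (66 cm") is marked for monocular and binocular testing at Month 1 and binocular testing at Month 3. One definition of distance correction covers the whole study.
- **Role of the Month 1 value (Section 5.C.2, item 4):** it appears only within a secondary endpoint, "Uncorrected and distance-corrected intermediate (66 cm) visual acuity at 1 and 3 months".
- **Analysis method (Section 5.B):** two-sided tests at 5%, with the choice of test left to the nature of the data. No primary model, analysis set or missing-data method is given.
- **Losses (Section 4):** patients may withdraw, be discontinued for missed visits, or be terminated after a severe, possibly related adverse event. Replacement is stated only for those discontinued before surgery.

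**The concern.** A two-sample t-test on Month 3 acuity uses only patients who have a Month 3 value. The plan expects about one patient in ten to be lost, and some of those will have been tested at Month 1. Their Month 1 acuity carries information about the missing Month 3 value, because it is the same quantity measured about two months earlier.

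Two things are at stake. The smaller is precision. The larger is protection against bias: patients are masked to group, but they know how well they see. If return at Month 3 depended on Month 1 vision, and did so differently in the two arms, the comparison of those who returned would be shifted, and the data needed to correct the shift would already be in hand. There is no preoperative DCIVA in Table 1, so Month 1 is the only other value of this outcome.

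**Working it through.** **1. Inputs.** From Section 5.A: SD 0.12, difference 0.1 logMAR, two-sided alpha 0.05, power 90%, 37 enrolled per group, 10% dropout. The text says that the estimates "depend in large part on the standard deviation (SD) for logMAR UCIVA", and the value is introduced as "Assuming a SD of 0.12 (from a previous Eyhance study"). It therefore refers to uncorrected acuity and is carried over to DCIVA here as an assumption. The Month 1 to Month 3 correlation r is not in the documents; 0.5 to 0.7 is assumed.

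**2. The plan's own figure.** n = 2(1.960 + 1.282)² × 0.12² / 0.1² = 30.3, so 31 per group. The exact noncentral t gives 32, and 31 gives 89.8% power. Enrolment: 62 + 6 + 6 = 74. The figure reproduces.

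**3. Month 3 t-test at the planned loss.** 37 × 0.9 = 33.3 per group observed. SE = 0.12 × √(2/33.3) = 0.0294. Power is 91.8%.

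**4. Two-visit model, random dropout.** With n₃ patients per group seen at Month 3 and n₁ seen at Month 1, the effective number per group is 1 / [(1 − r²)/n₃ + r²/n₁], and the SE ratio to the t-test is √(n₃ / effective n).

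| Dropouts with a Month 1 value | r | Effective n per group | SE reduction | Power |
|---|---|---|---|---|
| All (n₁ = 37) | 0.5 | 34.15 | 1.3% | 92.4% |
| All (n₁ = 37) | 0.7 | 35.02 | 2.5% | 93.0% |
| Half (n₁ = 35.15) | 0.5 | 33.74 | 0.7% | 92.1% |
| Half (n₁ = 35.15) | 0.7 | 34.18 | 1.3% | 92.4% |

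The formula treats the regression of Month 3 on Month 1 as known. Estimating it costs a little, so about 1% to 2% is a fair summary. At 15% dropout (n₃ = 31.45, all with Month 1, r = 0.7) the effective n is 33.94 and the reduction 1 − √(31.45/33.94) = 3.7%. A figure near 4% therefore needs more dropout than the plan assumes.

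**5. Bias if dropout in one arm depends on Month 1 acuity.** Let z be standardised Month 1 logMAR (higher is worse) and P(missing) = 1/(1 + exp(−(a + bz))) in one arm, with a set so that 10% are missing; dropout in the other arm is random. If the dropouts have mean z of m, those who stay have mean −0.1m/0.9, and the Month 3 mean in that arm shifts by 0.12 × r × (−0.1m/0.9).

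- b = 1.0 (a = −2.564, m = 0.817 by numerical integration): stayers' mean z = −0.0908. Shift = −0.0054 at r = 0.5 and −0.0076 at r = 0.7.
- b = 1.5 (a = −2.953, m = 1.095): stayers' mean z = −0.1217. Shift = −0.0073 and −0.0102.

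Simulation at 37 per arm gives 0.005 to 0.011 logMAR in size at 10% dropout and 0.007 to 0.015 at 15%. The Month 1-adjusted estimate is within 0.001 of the truth throughout.

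**6. Scale.** 0.005 to 0.011 is 5% to 11% of the 0.1 design difference. Against an SE of 0.0294, the closed-form shifts are 0.0054/0.0294 = 0.18 to 0.0102/0.0294 = 0.35 standard errors. By the normal approximation the two-sided type I error moves from 5% to Φ(−1.78) + Φ(−2.14) = 5.4%, up to Φ(−1.61) + Φ(−2.31) = 6.4%.

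**The case against.** The strongest reply is that the plan does not prescribe a complete-case analysis. A reader might infer that it does, from the t-test and the dropout allowance. The documents do not support that: the t-test is only the basis for sizing, Section 5.B leaves the method open, and no rule excludes patients without Month 3. Sizing on a t-test is compatible with analysing by a repeated-measures model. This stands. The defect is that the primary analysis and the handling of missing values are left unstated, and that the one test named would lose these patients if used.

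A reader might also infer that a biased result is likely. The documents give no reason to expect that either. Both arms receive the same lens, patients are masked and follow-up is three months. If the same dropout pattern held in both arms with equal SDs, the two shifts would be equal and cancel. The bias range is conditional on an assumed one-arm mechanism. This stands too.

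Third, a model using Month 1 might be read as unbiased in general. It is so only when missingness depends on observed values. A termination under Section 4 for an adverse event after Month 1 may change vision in a way that Month 1 cannot predict. Patients lost before Month 1 contribute nothing, and those whose surgery was aborted are already excluded from the efficacy analysis.

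Finally, power at the planned loss is already 91.8%, so the trial does not need the extra precision. That is correct, and it is why the point is an improvement rather than a flaw that threatens the result.

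**Conclusion.** The point holds as a modest, inexpensive improvement. Section 5 fixes neither the primary model nor the treatment of missing Month 3 values, and a better use of data already scheduled is available.

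Precision alone would hardly justify the change: power rises from 91.8% to 92.4% at r = 0.5 and 93.0% at r = 0.7 if every dropout has a Month 1 value. The better reasons are a prespecified method and protection against dropout related to Month 1 acuity. The sizes rest on an SD taken from uncorrected acuity, an assumed correlation and, for the bias, an assumed dropout mechanism in one arm; none of these can be checked from the documents. The endpoint, the time point and the sample size are not called into question by this point.

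**What to change.** State the primary analysis in Section 5.B as a likelihood-based repeated-measures model of binocular DCIVA at Months 1 and 3:

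- fixed effects for group, visit, group-by-visit and site (Section 5.A itself treats the two sites as a possible confounder);
- unstructured covariance, which with two visits has only three parameters;
- small-sample degrees of freedom such as Kenward-Roger;
- the group difference at Month 3 as the single primary contrast.

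Month 1 acuity is measured after treatment, so it enters as an outcome and not as a covariate. State that every randomised patient with an eligible DCIVA value at either visit is included, and that the model assumes missingness depends on observed values. Keep the Month 3 t-test as a sensitivity analysis, and report by arm the number and reasons for missing Month 3 values, separating losses before Month 1, which the model does not address.

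The cost is analysis-plan wording before the data are compared by group. No visit, measurement, endpoint or patient is added. The downside is a slightly less simple primary analysis. With no missing values, and apart from the site adjustment, its Month 3 estimate equals the simple difference in means.
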